Currently available evidence on dehydration in older people is patchy. It is vital for the health and wellbeing of older people, and to reduce unplanned emergency hospital admissions, that we identify dehydration in the community and residential care, and learn to prevent it. Our approach to develop the research base for water-loss dehydration is to assess the validity of these two short decision trees for use by care home staff. Validation is both essentialist (against the best reference standard of water-loss dehydration, serum osmolality), and consequentialist (assessing the utility of this panel in predicting mortality, functional status and QoL – using the data from the cohort element of the original DRIE study) (30). This will prepare for future randomised trials

of screening and intervention to prevent or redress impending water-loss dehydration on important health outcomes in older people. This part of the research is checking that the decision trees we created with care home residents are truly diagnostic.

Primary Aim:

The principal research objective is to test two short decision trees to assess whether either will usefully identify water-loss dehydration in frail older people.

Secondary aims:

Additional objectives include:

- 1. Assessing the acceptability and invasiveness of the individual assessments to older people living in residential care
- 2. To assess the relationship between nutritional status (assessed by change in weight over the past 6 months, body mass index, Mini Nutritional Assessment, Malnutrition Universal Screening Tool, haemoglobin) and hydration status in care home residents.
- 3. Assessing some additional promising clinical and/or physical signs or questions (such as assessing foot skin turgor, dry lips, asking participants whether they feel out of sorts, and whether they drink as much as they need to stay healthy, completing the mini-mental state exam, observing whether participants taste their drink immediately and recording their Barthel score and number of medications prescribed) so that if the current decision tree does not prove useful we have a strong evidence base (from 200 participants in the DRIE study, and a further 200 participants in DRIE 2) to allow development of a better decision tree.

Study design

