Reference standard data: serum osmolality, serum sodium, serum potassium, serum glucose (random) and serum urea, serum creatinine, liver function tests.

- Blood samples will be identified by study number, date and study name, date of birth and gender, and analysed at the Norfolk and Norwich University Trust Pathology laboratory (all samples will be delivered to the laboratory within 4 hours)
- Results will be returned to the CI
- Serum osmolality information will be interpreted and provided to the care home manager (or deputy) and the resident's general practitioner
- Blood samples will be destroyed after analysis within the laboratory
- We will request the following blood tests for each participant:
 - Serum osmolality (directly measured by freezing point depression)
 - o Urea and electrolytes (U/Es), including bicarbonate
 - Liver function tests (LFTs)
 - o Random blood glucose

Index tests (to use as described in the standard operating procedures of DRIE 2). The flow of the tests and questions will be roughly as follows (see 2 resident data collection form DRIE2 6April14 v1.0, but we will adapt this to improve the way that the testing works as necessary):

- 1. Start by moving to an appropriate location, ideally the resident's own bedroom, and ensuring that if they would like a care worker or family member with them that this has been organised (and that if they do not want anyone with them this is also ensured).
- 2. Resident is settled in a comfortable seat. During this time to have a general friendly chat as appropriate with the participant. Once settled to ask short questions about how the resident's occupation, education, marital status, whether they are feeling out of sorts, whether they have pain in their bladder or leak urine, whether they always drink as much as they would like to and drink first thing in the morning and at lunch time.
- 3. Take blood samples (once resident has been sitting for 5- 10 minutes to ensure standardisation), using needle and syringe, as taught by the Norfolk and Norwich University Hospital Phlebotomy department. Label and store all samples, dispose of all sharps as per SOP.
- 4. With resident still sitting conduct physical exams, assessing lip dryness, dryness of inside lower lip, skin turgor in back of hand and foot, crinkliness of skin on lower and upper inner arm, and ulnar length.
- 5. Conduct Mini-Mental State Exam (MMSE (32;33))

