- 6. Once participant has been sitting comfortably for at least 10 minutes measure blood pressure:
 - Assess blood pressure and pulse rate while sitting.
 - Help resident to stand in front of stable chair (using usual aids, help support them in case of dizziness), then measure BP after standing for 1 minute and 3 minutes. After the 1 minute measure ask if they feel dizzy or bad in any way (help them to a sitting position if any problems)

- While standing assess whether breathing is normal, deep or deep and rapid
- Ask whether the resident would mind if the care home staff assessed their sitting and standing blood pressures every few weeks
- 7. Ask the participants thoughts about the interview, whether they would find any of the tests annoying, painful or onerous if performed by care home staff every few weeks and ask them their ethnicity
- 8. Ask the participant for a urine sample help them to toilet (if help is needed), ask for a urine sample (collected in disposable "hat" in toilet). Help participant back to their preferred location in the home, make them comfortable with a drink and snack (where appropriate). Return to test urine:
 - Urine colour (against standard chart) and volume
 - Urine specific gravity (using dipstix), other dipstix measures
 - Urine specific gravity using refractometer
 - Urine volume (mls)
- 9. Help the resident back to their normal chair or position in the care home, and offer them a drink (or get the care staff to offer them a drink). Observe this process, including whether the participant tastes the drink immediately.

To ask of care home manager for each participating resident (see 1 CH re resident data collection form DRIE2 6April14 v1.0):

- Pre-interview check of exclusion criteria and blood test risks (including whether the
 participant has HIV or hepatitis, is on warfarin or steroids, their level of continence and
 whether either arm is unsuitable for taking blood or measuring blood pressure).
- Information on participant risk of dehydration, need for thickened drinks, whether the participant needs help to drink, equipment needed for drinking and questions relating to the Mini Nutritional Assessment (including recent reduction in food intake, psychological stress or acute disease, and mobility level)
- History of recent (over past week) vomiting, diarrhoea, cold, urinary tract infection (UTI) and/or fever
- Whether the participant appears well, out of sorts or ill today

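### In the listed interview flow the acceptability question comes before urine collection, so views on giving urine are anticipatory while views on the other tests follow experience

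*Protocol*

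**What the plan says.** Under Secondary aims, the first item in the protocol is "Assessing the acceptability and invasiveness of the individual assessments to older people living in residential care". It makes no exception for urine tests, and the Methodology section lists the urine measures among the index tests.

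The same section sets out the interview in nine steps. Step 7 is the general acceptability question. It reads "Ask the participants thoughts about the interview, whether they would find any of the tests annoying, painful or onerous", and it is framed as repetition of the tests by care staff at intervals of a few weeks. Step 8 begins "Ask the participant for a urine sample" and covers any help to the toilet, collection in a disposable container, the return of the resident, and then the researcher's readings of colour, volume and specific gravity. Step 9 is an observation of drinking.

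The one other acceptability item in the flow belongs to step 6 and concerns blood pressure only: "Ask whether the resident would mind if the care home staff assessed their sitting and standing blood pressures every few weeks". It follows the standing measurements.

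The list is not presented as binding. It opens with "The flow of the tests and questions will be roughly as follows" and adds "but we will adapt this to improve the way that the testing works as necessary".

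**The concern.** An aim that speaks of individual assessments invites a comparison between them: which ones residents would tolerate if care staff repeated them. That comparison is easier to read when every assessment has been judged from the same footing. In the listed order, urine collection is judged from a different footing than the rest.

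The procedure is not trivial for this population. The Background names incontinence and toilet access as issues in residents' decisions about drinking, and Safety considerations raises balance as a concern when urine is collected. The study also includes people with dementia by design, and the recruitment section expects that many residents may not clearly remember what they were told about the study. Imagining a procedure not yet carried out may be a weak substitute for being asked just after it.

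The result could matter later. Under Data analysis, if neither tree is useful, data on individual tests feed new combined tools. Urine measures could then be candidates, and how residents felt about giving the sample would be relevant.

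**Working it through.** No arithmetic applies: the point is about order and depends on no numerical input. The check sets the listed steps beside the aim.

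| Step | Content | Position relative to the general acceptability question |
|---|---|---|
| 2 | Short questions | Before |
| 3 | Blood sample | Before |
| 4 | Lip, mouth and skin examinations, ulnar length | Before |
| 5 | Mini-Mental State Exam | Before |
| 6 | Sitting and standing blood pressure, with its own acceptability item | Before |
| 7 | General acceptability question | n/a |
| 8 | Urine collection, then urine readings | After |
| 9 | Observation of drinking | After |

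1. *Is urine within the aim?* Yes. The aim covers the individual assessments, and urine is in the index-test list.
2. *Does any later item ask about it?* No. Step 8 has no acceptability item, and step 9 is an observation. The rest of the protocol gives no other acceptability question that covers urine.
3. *Is blood pressure treated differently?* Yes. It has its own item in step 6 in addition to step 7. Urine collection has no equivalent.
4. *What part of step 8 does the resident experience?* Only the collection. The resident is helped back before the researcher returns to read the sample, so colour, volume, dipstick and refractometer readings are not experienced in any order. One procedure is affected.
5. *What kind of answer does step 7 give?* The wording is hypothetical for every test, because it asks about future repetition by care staff. For steps 2 to 6 that forecast can draw on what has just happened. For urine collection, in the listed order, it cannot draw on the study sample.
6. *How many residents?* If the order is kept throughout, everyone who reaches step 7, out of a planned 200 recruits.

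**The case against.** The strongest reply is that the order is not fixed. The protocol calls it rough and reserves the right to adapt it. The working sequence will be set by the resident data collection form and by standard operating procedures that, under Quality assurance, are still to be rewritten with the tests in the correct order. Neither is available here. This stands as a limit. A reader might infer that no resident will ever be asked after giving urine, but the protocol does not support so absolute a statement. What remains is that nothing in it says the question will follow the sample, and unplanned reordering would mix anticipated and experienced answers.

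A second reply is that the question is hypothetical for all tests, so residents can still give a view on urine. That is correct. What is missing is recent experience of the procedure, not every possible answer. The unequal footing remains.

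A third reply concerns importance. Tree 1, as set out in the text, uses no urine test. The additional promising signs named in secondary aim 3 include none. The Background reports that several urine measures are not useful when relied on individually. This makes the consequence conditional and fairly remote, though the measures are still collected and a later combined tool could use them.

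A reader might also infer that the order flatters the urine tests, and put a number of percentage points on it. The documents support neither. Residents who worry about toilet access might expect more burden than they meet, or less. The protocol gives no acceptability rate, threshold or target from which a size could be derived.

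**Conclusion.** The point holds as a small mismatch between a stated aim and the way it is measured. If the listed order is followed, acceptability of urine collection rests on anticipation, while acceptability of the blood, skin, cognitive and blood pressure tests follows experience. Secondary aim 1 then does not compare them like for like.

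The scope is one procedure in one descriptive secondary aim. The accuracy of the decision trees, the sample size and the acceptability answers for the other tests already done are untouched. The direction and size of any bias are unknown. The conclusion assumes that the form and operating procedures keep the protocol's order and contain no later urine item. If they differ, the point reduces to aligning the protocol text with them.

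**What to change.** Keep step 7 where it is, for the tests already done. Add one short acceptability question about urine collection straight after step 8, in the same terms as step 7. Put it to all residents, including those who decline or cannot provide a sample. Record whether the sample was given, attempted or declined, and report urine-collection acceptability by that status. Restricting the report to residents who attempted a sample would drop those who refuse, who may be the strongest objectors.

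Make the change in the protocol flow, the resident form and the operating procedures before data collection, because a view taken just after the sample cannot be recovered later. The cost is one extra question, and a few residents may end the session after the toilet visit. Leaving step 7 in place protects the answers on the other tests from that loss.
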